7.12 Service utilisation questionnaire

Service utilisation questionnaire

1. **Have you been prescribed oxygen therapy?**

Yes No

2. **Over the last THREE months how often have you used oxygen on average while at home?**

- 4 times a day or more
- 2 or 3 times a day
- Once a day
- Less than daily

3. **Over the last THREE months have you carried portable oxygen with you when leaving your home?**

Yes No

4. **In the last THREE months have you used a rescue (blue) inhaler to help with your breathing?**

Yes No

5. **If YES, in the last THREE months how often have you used your rescue inhaler (blue inhaler) on average? Tick one box and give details of how often you use the inhaler.**

Every day

Please specify how many times a day you typically use your inhaler _____

Less than daily

Please specify how many times a week you typically use your inhaler _____

6. **In the last THREE months how many times have you been admitted to hospital?**

_____ times

Please give further information on each of your TWO longest hospital stays in this period starting with the longest stay

a. What was the reason for your longest hospital stay?

b. How long did you spend in hospital? _____ nights

c. What was the reason for your second longest hospital stay?

d. How long did you spend in hospital? _____ nights

7. In the last THREE months have you used the following health and social care services?

If yes please provide the following information.

Service	Tick box if service used	How many contacts / visits in the last THREE months?
a. Visits to a Hospital A & E Department		
b. Visits to a Hospital Outpatient Department		
c. Visits to General Practitioner at GP Practice		
d. Visit to Nurse at GP Practice		

8. In the last THREE months have you attended pulmonary rehabilitation classes?

Yes No

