2.1 Design, questions, aim and objectives

Design

The planned study is a single-blinded randomised controlled trial which will compare participation in a structured singing programme over 10 weekly sessions, with a usual treatment control. A 3 by 2 mixed anova design will be adopted with time as the within subjects factor at 3 levels (baseline, end of intervention and follow-up) and Condition as the between subjects factor with 2 levels (singing vs. control).

Questions

The study seeks to answer the following questions:

1. Is a ten-week progressively structured programme with recommended weekly practice between sessions acceptable, manageable and enjoyable for participants in the trial?
2. Does regular singing help to improve the perceived health and quality of life of patients with COPD over and above the provision of usual treatment?
3. Does regular singing result in a changed pattern of breathing in COPD patients with a shift towards breathing supported by the diaphragm, and a longer, slower controlled out-breath?
4. Does regular singing help patients with COPD manage the demands of daily living more effectively?
5. Does regular singing compared with usual treatment lead to a reduction in the use of medication and health services that will result reduced in care costs?

Aim and objectives

The overall aim is to conduct a pilot single-blinded randomised controlled trial, to evaluate the health benefits of a community singing group for patients with COPD in Medway, Kent. We are interested in finding out whether participating in community singing helps to improve the quality of life of patients with COPD.

Principal objectives are formulated around the primary outcome measure for the study, and a number of secondary outcomes. Service use will be assessed. There will also be an embedded qualitative study of patients' experiences of the singing programme, and the extent to which they follow guidance on practising breathing exercises and singing between group sessions.

Primary Outcome

- Impact on quality of life and management of breathing difficulties (as assessed by CAT) (Jones, et al., 2009; Kon, et al., 2014; Jones, et al., 2014; CAT, 2016)

Secondary Outcomes

- nMRC breathlessness scale (see: <https://mrc.ukri.org/research/facilities-and-resources-for-researchers/mrc-scales/mrc-dyspnoea-scale-mrc-breathlessness-scale/%EF%BB%BF> Williams, 2017; Fletcher et al., 1959)

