- SF-36 v2, Physical health related quality of life and Mental health related quality of life (Jenkinson et al., 1999) (Available from Optum: <http://campaign.optum.com/optum-outcomes/what-we-do/health-surveys/sf-36v2-health-survey.html>)
- Generalised anxiety disorder (as assessed by GAD-7) (Spitzer, et al., 2006)
- Depression (as assessed by PHQ-9) (Kroenke, et al., 2001)
- Anxiety (as assessed by GAD-7) (Kroenke, et al., 2002)
- Lung function and patterns of breathing (as assessed by spirometry and SLP – for further details see below)
Functional exercise (as measured by the 6MWT – further details below)
Use of inhalers, consultations with health professionals and hospital admissions

The standardised measures employed in this trial have been chosen based on previous research on singing and COPD, the outcome of recent systematic reviews (Lewis et al., 2016; McNamara et al., 2017, and the latest guidance on the assessment and diagnosis of COPD (NICE, 2018). All questionnaires have been screened and assessed for suitability as ‘patient reported outcome’ measures using the checklist devised by Francis et al. (2016) (see Appendix 7.10).

We are using CAT, GAD-7 and PHQ-9 as these measures are routinely used by the Medway Community Healthcare Respiratory team in the monitoring of responses to pulmonary rehabilitation.

CAT serves as a COPD-specific quality of life measure and is especially suited to being the primary outcome measure for the study. There is also an established ‘minimum clinically importance’ change score of two points (Kon et al., 2014), and this will provide an important criterion against which to judge the outcome of the trial for clinical purposes.

Both GAD-7 and PHQ-9 have established cut-off points for increasing grades of severity on mental health condition, and will serve to assess the extent to which participants in the trial can be regarded as experiencing clinically significant levels of mental health challenge, and whether this changes over the course of the trial for the intervention group relative to the control. It is recognised also that the two mental health scales can be combined to form a single measure of anxiety-depression.

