2.6 Data Collection

Participants will be invited to attend for assessments three times over the course of the project (baseline, end of intervention, further three months follow-up). It is expected that one hour to an hour and a half, will be needed for the physical assessments and completion of questionnaires. Participants will arrive at the baseline assessment session and informed consent taken, and a safety check will be made regarding their suitability for the physical assessments (health screening questionnaire, resting heart rate and oxygen saturation, and blood pressure). They will then complete the written questionnaires before undertaking the physical assessments in a structured sequence:

The following demographic details and information on health service use will be collected for all participants as the first part of an assessment questionnaire:

- Gender
- Age
- Ethnicity
- Marital status
- Employment/volunteer status

- Smoking status
- COPD diagnosis (date and severity)
- Details of PR attendance
- Co-morbid conditions
- Medication and health service use (use of inhalers and home oxygen, primary care consultations and hospital admission over the previous three months)
- Frequency and severity of exacerbations (over the previous three months)

Questionnaires

The quantitative data will be collected from both the singing group and the participants at baseline, and conclusion of the programme at three months, and on follow-up at six months. Participants will be asked to complete the following collection of questionnaires:

- COPD Assessment Test (CAT)
- MRC breathlessness scale (MRC)
- SF-36v2 (physical and mental health related quality of life)
- GAD-7
- PHQ-9

All of these questionnaires are simple, short and straightforward. It is anticipated that they will take 20 minutes to complete. Support will be available if participants need help in completing the questionnaires.

Exercise assessment and Spirometry

The following measures will be taken on the basis of physical examination:

- Weight and height (to allow for BMI)
- FEV1 (plus percentage)
- FVC (plus percentage)
- Expiratory pressure
- Chronic hypoxia and/or cor pulmonale
- Transfer factor for carbon monoxide (TLCO)

- Breathing patterns assessed with Structured Light Plethysmography (SLP) before and after the 6-minute walk test
- Exercise capacity assessed by 6-minute walk test (6MWT)

Procedure

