2.8 Data Analysis

The design of the trial is a 3 by 2 mixed anova design with time as the within subjects factor at 3 levels (baseline, end of intervention and follow-up) and Condition as the between subjects factor with 2 levels (singing vs. control). The primary outcome variable for the trial will be the COPD Assessment Test score. Additional secondary analyses will consider a range of additional health measures, together with spirometry, exercise and SLP parameters. We will also examine differences between the intervention and control groups on indicators of service use to determine potential cost-savings associated with reduced inhaler usage, consultations with health professionals and hospital admissions. Embedded within the trial will be a qualitative assessment of the participant experience and perceived benefits, together with an evaluation of the resources to support practice between singing sessions.

Quantitative data

Quantitative data will be analysed using IBM SPSS 24. Comparative analysis will take place to examine composition of the intervention and control groups at baseline to assess equivalence. Comparisons will be made between the intervention and control groups at two follow up points to

determine whether the intervention has resulted in significant change on the primary and secondary outcome measures, which allow for rejection of the null hypothesis that singing results in no change in functional status, health related quality of life, mental wellbeing and patterns of breathing. Appendix 7.11 provides a plan for the statistical analysis to be undertaken, and considerations of effect size and power, provided by the project statistical consultant [name].)

Qualitative data

For the qualitative data obtained from individual interviews, thematic analysis (Braun and Clarke, 2006) will be used to identify any consistent themes. The qualitative data will be analysed using QSR International's NVivo 11 software. Within NVivo, queries will be run to determine word frequencies within respondents' qualitative comments.

For the thematic analysis, this process has six phases:

- Familiarising yourself with your data: Transcribing data (if necessary), reading and re-reading the data, noting down initial ideas.
- Generating initial codes: Coding interesting features of the data in a systematic fashion across the entire data set, collating data relevant to each code.

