7.6 Participant personal information questionnaire

Participant personal information questionnaire

Name _____

Age _____

Address

Name and address of your GP _____

1. What is your sex? Please circle: Male Female

2. What is your marital status? Please circle:

Single/Unmarried

Married

Same-sex civil partnership

Separated but still legally married or legally in civil partnership

Divorced

Widow/widower (including from civil partnerships)

3. How would you describe your national identity? Please circle:

British

English

Northern Irish

Scottish

Welsh

Another Nationality – Please describe here: _____

4. What is your ethnic group?

Choose one section from A to E, then circle one to best describe your ethnic group or background

A. White

English/Welsh/Scottish/Northern Irish/British

Irish

Gypsy or Irish Traveller

Another white background

B. Mixed/multiple ethnic groups

White and Black Caribbean

White and Black African

White and Asian

Another mixed/multiple ethnic group

C. Asian/Asian British

Indian

Pakistani

Bangladeshi

Chinese

Another Asian background

D. Black/African/Caribbean/ Black British

African

Caribbean

Another Black/African/Caribbean/ Black British

E. Another ethnic group

Arab

Another ethnic background

5. Have you received a formal diagnosis of COPD? Yes No

**6. Have you undertaken pulmonary rehabilitation
in the last THREE months?** Yes No

7. If yes, how many sessions did you attend? _____ sessions

8. How would you describe your level of COPD currently?

Mild

Moderate

Severe

Very severe

**9. Have you experienced any significant worsening
of your COPD over the last THREE months?** Yes No

10. Are you affected by other health conditions? Yes No

9. If yes, please describe here:

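### The service-use form covers only the rescue inhaler and the exacerbation item is yes/no, so neither overall inhaler use nor exacerbation frequency can be derived

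*Protocol*

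**What the plan says.** Three places in the protocol set out what is to be learned about medication:

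- Question 5 in section 2.1 asks whether singing will "lead to a reduction in the use of medication and health services that will result reduced in care costs".
- The last entry in the list of secondary outcomes in 2.1 is "Use of inhalers, consultations with health professionals and hospital admissions". It is not limited to one type of inhaler.
- Section 2.8 plans to compare the arms on service use to find "potential cost-savings associated with reduced inhaler usage, consultations with health professionals and hospital admissions".

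The instrument is the service utilisation questionnaire in 7.12. Its inhaler items name the rescue (blue) inhaler only. Daily users are told: "Please specify how many times a day you typically use your inhaler". Less frequent users give a number per week. Oxygen has a prescribed yes/no item, and then "Over the last THREE months how often have you used oxygen on average while at home", answered in four frequency bands.

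On exacerbations, the data list in 2.6 includes "Frequency and severity of exacerbations (over the previous three months". The matching item is in the personal information questionnaire (7.6). It begins "Have you experienced any significant worsening" and is answered Yes or No for the last three months.

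**The concern.** The outcome, question 5 and the costing are worded for inhalers or medication in general, while the form records one inhaler type. Section 1.1 itself describes inhaled COPD treatment as including bronchodilators, steroids and combination products, so the protocol recognises inhalers that its form does not ask about. The exacerbation entry promises a frequency and a severity, while the form yields a single binary answer.

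Both gaps lie in data collection. A statistical analysis plan can define derivations and models, but it cannot recover what was never asked. At stake are the inhaler outcome, the answer to question 5, the inhaler part of the cost comparison and the exacerbation description.

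**Working it through.** The protocol gives no figure to reproduce here, so the check sets what is promised beside what is collected.

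**1. Is medication quantified anywhere else?**
- Personal information questionnaire (7.6): no medication item.
- Home practice diary (7.17): attendance, practice, songs, time and comments only.
- Interview schedules (7.16): an open question on change in medication use. Section 2.6 gives these interviews to a sample, once, after the final data collection, so they supply no quantity and no baseline.

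Section 7.12 is therefore the only quantitative source.

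**2. What can a cost be built from?** Write the change in inhaler cost for one participant as

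ΔC = c_r·ΔA_r + Σ c_m·ΔA_m

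where A_r is the amount of rescue inhaler used, A_m the amount of each other inhaler, and c the unit costs.

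- The form has no item for any A_m, so the second term is set to zero for everyone, whatever happened.
- For the rescue inhaler, amount = uses × puffs per use. The form records uses (U) but not puffs per use (p). The recorded ratio is U2/U1, while the ratio in amount is (U2·p2)/(U1·p1). They agree only when p1 = p2.

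**3. What does this do to the comparison between arms?** The omitted part of the difference is the mean of Σ c_m·ΔA_m in the singing arm minus the same mean in the control arm. It is zero if other inhalers change equally in both arms, and otherwise positive or negative. The documents give no data on either mean, so neither sign nor size can be stated. A move between rescue and other inhalers that differed by arm would appear as a saving or a cost from the rescue part alone.

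**4. Exacerbations.** The 7.6 item separates none from one or more. Counts of 1, 2 and 3 all give Yes, so a fall from 3 to 1 is recorded as no change and no frequency can be derived. The item does not ask severity either. Section 7.12 collects the number of admissions, reasons and nights for the two longest stays, and counts of A&E, outpatient, GP and practice nurse visits. These bear on severity for events that led to such contact, but they do not count exacerbations.

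**5. Oxygen.** Item 1 of 7.12 identifies people not prescribed oxygen. Item 2 then has no If YES lead-in (item 5 has one), no option for none and no duration. Oxygen is in the 2.6 data list and can be read into question 5, but it is in neither the secondary outcome entry nor the costing sentence in 2.8.

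**The case against.** A fair defence is that this is a self-described pilot, the primary outcome is the CAT, and the text speaks of use, which frequency can reasonably represent. The rescue item is an open count that converts to uses per week and is a workable rough proxy. That stands: rescue-inhaler frequency is usable under its own name. It does not make one inhaler type stand for all inhalers.

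It can also be said that exacerbations are not a listed outcome and do not enter the cost figure. That is correct and keeps this part small, but the mismatch between 2.6 and 7.6 remains.

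Four stronger readings are tempting, and the documents do not support them:

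- **That the form will show false reductions.** Someone going from 4 uses of 2 puffs to 2 uses of 4 puffs takes 8 puffs both times while the count falls by 50%. These values are invented. Nothing in the protocol suggests such a switch, still less in one arm only.
- **That oxygen users are ranked in the wrong order, by more than tenfold in hours.** This needs assumed session lengths. The share of participants on oxygen is not given, and misordering different people does not by itself bias a randomised comparison of change.
- **That people not using oxygen have no valid answer.** Item 1 lets those without a prescription say so. What is left is a missing skip instruction and, for prescribed non-users, a missing none option.
- **That leaving out oral steroid and antibiotic courses is an error.** The bracket in 2.6 spells out medication and service use as inhalers, home oxygen, primary care consultations and hospital admission. Adding such courses would widen the scope, not correct a contradiction.

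**Conclusion.** Two mismatches hold. First, 7.12 can support a statement about how often the rescue inhaler is used, but not about use of inhalers overall, medication as question 5 words it, or an inhaler cost-saving expressed as an amount. Second, 7.6 cannot supply the exacerbation frequency that 2.6 lists.

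The size and direction of any error cannot be given, because the protocol has no figures on other inhaler use, puffs per use or exacerbation rates. The inhaler conclusion assumes that the appended forms are the ones used and that no medication record is taken from elsewhere; the protocol mentions none. The CAT analysis is not affected. The oxygen layout is a minor matter. The point is worth correcting because the forms fix it permanently once data collection starts, but it carries modest weight.

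**What to change.** **In 7.12:**
- Add an item on other prescribed inhalers: name and usual puffs per day.
- Add usual puffs per use to item 5, so that inhaler use can be costed as an amount.
- If the sponsor prefers not to lengthen the form, reword the secondary outcome, question 5 and the costing sentence in 2.8 so that they refer to rescue-inhaler frequency only.
- Minor: put If YES before oxygen item 2, add a none option and ask hours per day.

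**In 7.6:**
- Replace the yes/no item on worsening with the number of exacerbations in the last three months and, for each, whether it led to treatment or admission. Two items in 7.6 carry the number 9; this is the first of them.
- Ask it at all three assessments, and say so in 2.6. The five questionnaires that 2.6 names for the three time points do not include it.

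The cost is a few short items on a self-completed form, a slightly longer completion time and some recall error. Section 4.1 places baseline assessments in July 2019, after this December 2018 version, so on the protocol's own timetable the forms can be changed before first use. The changes concern measurement only.

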7.13 Checklist for the suitability of patient-reported outcome measures (Francis et al., 2016)

CONCEPTUAL MODEL
1. Has the PRO construct to be measured been specifically defined?
2. Has the intended respondent population been described?
3. Does the conceptual model address whether a single construct/scale or multiple subscales are expected?
CONTENT VALIDITY
4. Is there evidence that members of the intended respondent population were involved in the PRO measure's development?
5. Is there evidence that content experts were involved in the PRO measures's development?
6. Is there a description of the methodology by which items/questions were determined (e.g. focus groups, interviews)?
RELIABILITY
7. Is there evidence that the PRO measure's reliability was tested (e.g. test-retest, internal consistency)?
8. Are reported indices of reliability adequate (e.g. ideal: $r \geq 0.80$; adequate: $r \geq 0.7$; or otherwise justified)?
CONSTRUCT VALIDITY
9. Is there reported quantitative justification that single scale or multiple subscales exist in the PRO measure (e.g. factor analysis, item-response theory)?
10. Are there findings supporting expected associations with existing PRO measure or with other relevant data?
11. Are there findings supporting expected differences in scores between relevant known groups?
12. Is the PRO measure intended to measure change over time? If YES, is there evidence of test-retest reliability and responsiveness to change?
SCORING AND INTERPRETATION
13. Is there documentation how to score the PRO measure (e.g. scoring method)
14. Has a plan for managing and/or interpreting missing responses been described (i.e. how to score incomplete surveys)?
15. Is information provided about how to interpret the PRO measure scores (e.g. scaling/anchors (what high and low scores represent), normative data and/or a definition of severity (mild to severe))?
RESPONDENT BURDEN AND PRESENTATION
16. Is the time to complete reported and reasonable?
17. Is there a description of the literacy level of the PRO measure?
18. Is the entire PRO measure available for public viewing (e.g. published with the citation, or information provided about how to access a copy)

7.14 – Statistical Analysis Plan

Design	3x2 mixed anova				
factors	levels	measurement			
Time	3 (T1, T2, T3)	within subject/repeated measures			
Condition	2 (Intervention, TaU)	between subjects			
effect/analyses	expected difference	Notes	required N for minimum .80 power and alpha at .05 with moderate effect size d=.5		
anova - main effect of time	not relevant		34		
anova - main effect of condition	not relevant		86		
anova - interaction	significant		36		
anova - main effect of condition within T1	non significant		146	Bonferroni corrections included	sensitivity power analyses revealed that the minimum effect size detectable with power of .80 and sample size of 40 in each group is d=.68
anova- main effect of condition within T2	significant	the effect sizes of these two effects can be compared to test for prolonged effects of the intervention	146	Bonferroni corrections included	
anova - main effect of condition within T3	significant (but smaller than above)		146	Bonferroni corrections included	
anova - main effect of Time within Intervention Condition	significant		28		
anova - main effect of Time within TaU Condition	non significant		28		
anova - post hoc on main effect of Time within Intervantion Condition	significant between T1 and T2 but possibly disappearing between T2 and T3		39	Bonferroni corrections included	
anova - post hoc on main effect of Time within TaU Condition	not relevant		39	Bonferroni corrections included	

7.15 – Medway Singing and COPD Programme

The design of the singing programme is based on facilitator experience and participant feedback from singing for health projects conducted by the Sidney De Haan Research Centre over the past ten years. Each session will commence with physical and vocal warm-ups to prepare and protect the voice. These range in intensity and demand and are designed to provide a common focus, as well as encourage participants to learn to gain control of their breathing prior to singing.

Participants will be guided through a variety of songs, which gradually demand greater breath control and vocal production during the course of the singing sessions. Repertoire will include songs with short and long phrases, and a blended approach in each session will encourage confidence and breath-control. In addition, material will be utilised which encourages strong diction and vocal projection, both of which require consideration of breath control and management. Potential limitation in vocal range will be carefully addressed, with consideration given to the key and notation range in each song.

Singing is often a trigger for emotional release, and consideration will be given to the focus of songs chosen, with avoidance of highly emotive subject matter. The range of songs will incorporate popular, national and world music, including those likely to be at least partly familiar participants as well as new material. The use of well-known material encourages greater confidence with singing and avoids spending much time learning new melodies. However, if appropriate, harmonies and creative performance will be encouraged.

Participants will also be encouraged to use the Singing for Better Breathing Resource, which will enable them to practise additional songs in between sessions. Use of the resource gradually demands greater breath control and vocal strength and supports the development of the individual singer during the course of the project.

Issues targeted in the programme	Symptoms / issues	Musical intervention	Activity or songs
Phonation	Breathy voice quality Weakened vocal anatomy Side-effects of inhaler use (hoarseness)	Breathing technique, velum exercises (e.g. tongue tip to soft pallet, sound ka, ga), group chanting, use of crescendo	Banaha, Swing Low, When All the Saints, She'll Be Coming 'Round the Mountain medley
Articulation	Weak articulatory muscles	Steady rhythmic pieces	Swing Low, When All the Saints, She'll Be Coming 'Round the Mountain medley
Breathlessness and the fear of breathlessness	Breathlessness on exertion and/or at rest	Breath-control warm-up exercises. Exercises to encourage deep breathing with controlled exhalation. Songs which encourage full	Fizz and Blow exercise. Counting on exhalation. Full inhalation followed by upper and lower tone laughter. Pick A Bale A Cotton, Whip Jamboree

		exhalation followed by quick 'muscular' inhalation.	
Coughing	Cough on inhalation and exhalation	Encourage nasal inhalation to warm air and avoid trigger of cold air on cough reflex	
Generalised muscle weakness	Immobility, falls, loss of intercostal muscle strength	Core strength, rhythmic stepping	Songs with a marching beat or strong rhythm e.g. I'd Like To Teach The World To Sing
Attention	Lethargy, withdrawal	Motivation, energising accessible material with appropriate challenge	Energizing songs, e.g. I Got Rhythm
Depression	Misery, poor motivation, lethargy, carer stress	As above	Depending on mood, either uplifting, energizing or thoughtful songs e.g. Lean on Me
Anxiety	Acute distress, hyperventilating, rapid pulse rate, carer stress	Group security, bonding, relaxation	Songs which focus on community, friendship and welcome e.g. Senwa De Dende, Consider Yourself
Social isolation	Loneliness, withdrawal, carer stress	Social bonding, motivation, group security	Songs which focus on community, friendship and welcome e.g. Senwa De Dende, Consider Yourself

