1.6 Rationale and hypotheses for the current study

The conclusion of reviews of research supports the need for further research in the form of randomised controlled trials, as do the recommendations from the studies cited above. The proposed study will be larger than previous studies and include assessment of change on the primary outcome measure of COPD specific health status (the COPD Assessment Test, CAT), immediately after a three-month programme of regular singing, and on further three month follow up. The primary research null hypothesis will be that: 'No change occurs in COPD-specific health status, following ten weeks of regular, weekly singing at the primary end point for the trial six months post-baseline.'

A particular challenge is establishing real-time records of patterns of respiratory function to test a secondary hypothesis that regular singing leads to change towards deeper breathing supported by the diaphragm. One technique which may do this is structured light plethysmography (SLP) where movements of the chest wall and abdomen can be recorded for individuals as participants' breath. A small, feasibility exercise assessing the value of this technique for the current study has been undertaken (see above). The supplementary null hypothesis will be that: 'No changes occur in key parameters (specified below) derived from structured light plethysmography reflecting movement of the chest and abdomen during breathing, following three months of regular singing, at the primary end point of the trial six months post-baseline.'

Further secondary hypotheses will be tested for potential changes three months post-baseline at the conclusion of the singing programme.

Singing and COPD protocol version 1, 18 December, 2018

As, following randomisation, participants will inevitably be fully aware of their allocation to singing group or control, the trial cannot be double-blinded. However, in follow-up assessments, the staff conducting the measurement procedures will be blind to trial allocation.

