- The Medway feasibility study (see above) showed an improvement on the CAT questionnaire of five points, more than twice the minimum clinical difference score of two. A change of five points represents a moderate effect size of approximately 0.5. If such a difference arises between the intervention and control groups in the proposed trial, where data is paired from pre-test and follow up, a sample size of 40 per group will be more than sufficient to give 90% power at a p-value of 5% (two-tailed) (Chan, 2003).
-
- The proposed study will assess participants immediately following the intervention and then after a further three months. No such follow-up has taken place in previous trials.

- The current study is a pilot and if the findings are encouraging the results could be subsumed into a larger multi-centre trial conducted in the same way.

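### Appendix 7.14: the Bonferroni rows (146, d=.68, 39) fit only an undeclared one-sided alpha of about .016, and the interaction N of 36 matches neither the table's other rows nor a between-arm difference of d=.5

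*Protocol*

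**What the plan says.** The table in Protocol Appendix 7.14 describes the design as a "3x2 mixed anova" with three visits (T1, T2, T3) and two arms. One column gives the "required N for minimum .80 power and alpha at .05 with moderate effect size d=.5". The rows that matter here are:

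- Condition within T1, within T2 and within T3: 146 each, marked "Bonferroni corrections included".
- Post hoc time contrasts within an arm: 39, with the same mark.
- A note beside the 146 rows: "sensitivity power analyses revealed that the minimum effect size detectable with power of .80 and sample size of 40 in each group is d=.68".
- The row "anova - interaction": 36. It is expected to be significant and carries no Bonferroni mark.
- Other rows: condition 86, time 34, time within each arm 28.

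The table expects no arm difference at T1, a difference at T2 and a smaller one at T3. It states no sidedness, Bonferroni divisor or between-visit correlation, and does not say whether each N is a total or per arm.

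Elsewhere, Section 2.2 plans 40 analysed per arm and makes a separate power statement for paired data with "90% power at a p-value of 5% (two-tailed" as its terms. Section 1.6 words the primary null as "No change occurs in COPD-specific health status, following ten weeks of regular, weekly singing", assessed six months after baseline.

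**The concern.** All three Bonferroni-marked figures are smaller than a two-sided test at .05/3 would need. The interaction figure is smaller still, although an interaction that starts from no baseline difference is usually hard to detect.

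The interaction is the one omnibus effect the table expects to be significant; both main effects are marked as not relevant. A reader who sees 36 against 80 planned patients will conclude that the key test has more than twice the sample it needs. Section 2.2 also says the results could feed into a larger multi-centre trial, which might carry these figures forward.

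**Working it through.** **Inputs.** Power .80, alpha .05 and d=.5 (Appendix 7.14). 40 per arm (Section 2.2). A Bonferroni divisor of 3 is assumed, from three visits or three pairwise time contrasts. The between-visit correlation ρ is not stated, so a range is shown. Equal SDs, equal correlations and sphericity are assumed.

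**1. Bonferroni rows.** Noncentral t. Two arms with n each: noncentrality d√(n/2), df 2n−2. Pairs: noncentrality d√n, df n−1.

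| Alpha | Total N, d=.5 | Minimum d at 40 per arm | Pairs, d=.5 |
|---|---|---|---|
| Printed | 146 | .68 | 39 |
| One-sided .016 | 146 | .678 | 39 |
| One-sided .05/3 | 144 | .674 | 38 |
| Two-sided .05/3 | 172 | .737 | 45 |
| Two-sided .05/2 | 156 | .70 | 41 |
| Two-sided .05, no correction | 128 | .634 | 34 |

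One-sided .016 is .05/3 truncated. Read as a two-sided level it is .032, and .05/.032 = 1.56 is not a whole-number Bonferroni divisor.

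Power of the printed figures at two-sided .05/3:
- 73 per arm, d=.5 (noncentrality .5√36.5 = 3.02): 72.5%.
- 40 per arm, d=.68 (.68√20 = 3.04): 72.3%.
- 39 pairs, d=.5 (.5√39 = 3.12): 72.9%.

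**2. Rows that reproduce.** Noncentral F with f = d/2 = .25, m = 3 visits and ρ = .5.
- Condition: λ = f²Nm/(1+(m−1)ρ). At N=86 this is .0625×86×3/2 = 8.06, and the required N is 86, as printed.
- Time within one arm: λ = f²Nm/(1−ρ). At N=28 this is .0625×28×3/.5 = 10.5, and the required N is 28, as printed.

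**3. Interaction row, same settings.** λ = f²Nm/(1−ρ) with df 2 and 2(N−2). The required N is 28, not 36. At f=.25 and ρ=.5, N=36 has 90.6% power. It is the required N only if a setting is changed, for example power .90, alpha .0167, a sphericity epsilon of .7, or three groups.

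**4. What d=.5 means for the interaction.** With arm differences Δ at T1, T2 and T3, f = √[mean of ((Δ − mean Δ)/2)²].
- (0, .5, .5): mean .333, halved deviations −.167, .083, .083, so f = .5/√18 = .118.
- (0, .5, .25): mean .25, halved deviations −.125, .125, 0, so f = .5/√24 = .102.
- Conversely, f=.25 needs d = .25√18 = 1.06 (equal at T2 and T3) or .25√24 = 1.22 (halved at T3).

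Required total N, and power at N=36 and N=80 (alpha .05):

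| ρ | (0, .5, .5): N | at 36 | at 80 | (0, .5, .25): N | at 36 | at 80 |
|---|---|---|---|---|---|---|
| .3 | 164 | .23 | .48 | 218 | .18 | .37 |
| .5 | 118 | .31 | .62 | 156 | .24 | .50 |
| .65 | 84 | .43 | .79 | 110 | .33 | .66 |
| .7 | 72 | .49 | .85 | 96 | .38 | .73 |
| .85 | 38 | .80 | .99 | 48 | .67 | .96 |
| .9 | 26 | .93 | 1.00 | 34 | .84 | 1.00 |

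So 36 fits a d=.5 arm difference only at ρ of about .85 or more if the effect is held at T3, and nearer .9 if it is halved.

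**The case against.** - **Sidedness is inferred.** Appendix 7.14 is silent, and the two-tailed wording in Section 2.2 belongs to another calculation. The value .016 is found by fitting. This stands as a limit, but one setting recovers three separate figures, and the non-directional null and the ANOVA labels both point to two-sided tests.
- **The source of 36.** A reader might infer that it comes from treating f=.25 as d=.5. The documents do not show this: that route gives 28, and several altered settings give 36. Its origin is unknown.
- **Fixed replacements.** A reader might want to print 118 or 84 instead. Both assume equal effects at T2 and T3, whereas the table expects T3 to be smaller, and both depend on a correlation the protocol never gives. At ρ of .7 or more, 80 patients exceed 80% power for (0, .5, .5), so it cannot be said outright that the interaction is under-powered.
- **Detecting d=.68.** It would be too strong to say that 40 per arm cannot detect it. If the single six-month contrast is tested alone at two-sided .05, power for d=.68 is 85%.
- **Consequence.** Section 2.2 says resources, not a formal calculation, set the sample size, and it acknowledges possible under-powering. The table already shows 146 and 86 against 80. This stands and limits the severity.

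**Conclusion.** The point holds for the Bonferroni-marked figures and the interaction row. With two-sided tests at .05/3, the former understate the requirement by 26 patients in total (172 against 146), by .06 in detectable d (.74 against .68) and by 6 pairs (45 against 39). The interaction N of 36 is inconsistent with the table's own 86 and 28 rows and is not a d=.5 figure unless between-visit correlation is very high. At ρ=.5, the value those rows imply, N=80 gives 62% power, or 50% if the T3 effect is halved.

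A reader might conclude that the whole column is wrong or that the trial must be resized. Neither follows. Rows 86 and 28 reproduce, and the sample size never rested on this table. The time row (34) does not reproduce at the same settings, which give 28, so its assumptions should also be stated. This should be fixed but does not block the trial. The main gain is to remove the false comfort of 36 against 80.

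**What to change.** In Appendix 7.14:

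1. State two-sided alpha .05/3 for the Bonferroni rows. Replace 146 with 172 (86 per arm), .68 with .74 and 39 with 45. If the six-month primary contrast is to be tested alone at two-sided .05, give 128 and d=.63 for that contrast.
2. Replace 36 with a range that names the mean pattern and correlation. For (0, .5, .5): 118, 84 and 72 at ρ of .5, .65 and .7. For (0, .5, .25), which suits the expected smaller T3 effect: 156, 110 and 96.
3. Give interaction power at 80 analysed for the same three correlations: .62, .79 and .85 for the first pattern; .50, .66 and .73 for the second.
4. Label every N as total, per arm or pairs, and state the settings behind the 34. Keep 86 and 28.

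The cost is about an hour of recalculation and a change of appendix wording. Recruitment and trial procedures are unaffected.
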